4.8.2.2 Deaths

The following death summaries will be generated on the safety analysis set.

- Number (%) of patients who died during the study and reasons for death

- Number (%) of patients who died within 30 days after last dose of study drug except deaths occurred after taking any subsequent anticancer therapy/procedure and reasons for death

All deaths will be listed.

4.8.3 Laboratory Data

Laboratory data of hematology, chemistry, and coagulation will be reported in SI units.

Descriptive statistics (mean, standard deviation, median, and range) will be calculated for the raw data and for their changes from baseline at each scheduled assessment.

All results will be summarized using shift from baseline. Shifts for clinical laboratory results that can be graded according to CTCAE version 4.0 will be summarized by CTCAE grade.

Summaries by visit will include data from scheduled assessments, and all data will be reported according to the nominal visit date for which it was recorded. Unscheduled data will be included in “worst case post-baseline” summaries, which will capture a worst case across all scheduled and unscheduled visits after the first dose of study treatment.

Summary analyses will include data up to the start of subsequent anticancer therapy/procedure.

All laboratory data, including urinalysis, will be listed. Pregnancy test results will not be listed, but will be included in datasets.

4.8.4 Electrocardiogram

Electrocardiogram (ECG) parameters (e.g., corrected QT interval [QTc] in ms) will not be converted or derived, but will be reported as provided by investigational sites.

Descriptive statistics (mean, standard deviation, median, and range) will be calculated for the raw data and for their changes from baseline at each scheduled assessment.

The following abnormal QTc (including QTcF, QTcB and QTc with unspecified method) will be reported:

At any post-baseline with absolute value

>450 - <=480 ms

>480 - <=500 ms

> 500 ms

Change from Baseline

>30 – <=60 ms

>60 ms

For patients with unspecified QTc method at either baseline or post-baseline, consistent correction method is assumed within a patient when calculating the change from baseline.

Summary analyses will include data up to the start of subsequent anticancer therapy/procedure.

All ECG data will be listed, both for quantitative data and for overall impression.

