8.3.7 ECG

Three consecutive (also called triplicate) 12-lead ECGs will be performed at defined timepoints throughout the study as per SoE ([Table 1](#)). Refer to [Table 4](#) for the detailed schedule of ECGs.

ECGs should be performed after the patient is resting for at least 5 minutes.

Where applicable, at timepoints coinciding with blood sample collection including PK, ECGs should be taken prior to blood collection and before vital sign measurements.

If a patient experiences Torsade de Pointes, additional concomitant PK samples (i.e., unscheduled) should be collected.

Table 4 Schedule for Triplicate ECG Collection

| Cycle | Day | ECG timepoint (window) |
|-------------|-----|---|
| Screening | - | Any time within 28 days prior to C1D1 |
| C1 | D1 | Pre-dose (preferably within 2 h prior to start of infusion) EOI (within 10 min prior to EOI) Post-dose* 4 h (\pm 15 min) |
| | D8 | Post-dose* 168 h (\pm 48 h; but within 30 min prior to PK sample) |
| | D15 | Post-dose* 336 h (\pm 48 h; but within 30 min prior to PK sample) |
| C2 | D1 | Pre-dose (within 30 min prior to PK sample) EOI (within 10 min prior to EOI) Post-dose* 4 h (\pm 15 min) |
| | D8 | Post-dose* 168 h (\pm 48 h; but within 30 min prior to PK sample) |
| | D15 | Post-dose* 336 h (\pm 48 h; but within 30 min prior to PK sample) |
| C3 | D1 | Any time (but within 30 min prior to PK sample) |
| EOT | | Any time (but within 30 min prior to PK sample) |
| Unscheduled | | Any time |

Abbreviations: ECG, electrocardiogram; EOI, end of infusion; EOT, end of treatment; PK, pharmacokinetics.

*Post-dose timepoint is counted from start of Loncastuximab tesirine infusion.

Eligibility and clinical decisions may be made based on the local ECG assessment. ECGs will be submitted for a central review. Submission instructions for the central review will be provided in a separate manual. Assessments will include determination of heart rate and rhythm and the PR, QRS, QT, QTcF), and QTcB intervals.

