4.8 Safety Analyses

The summary of safety results will be presented by treatment group.

General common rules

All safety analyses will be performed on the safety analysis set, unless otherwise specified, using the following common rules:

- The baseline value is defined as the last non-missing value or measurement taken up to the first dose in the study.
- The analyses of the safety variables will be essentially descriptive and no systematic testing is planned.
- The toxicity grade according to the Common Terminology Criteria for Adverse Events (CTCAE) version 4.0 will be taken into account in the summary. For patients with multiple occurrences of the same event, the maximum grade is used. If a patient has both missing and non-missing severity grades for treatment-emergent adverse events (TEAEs) within the same preferred term (PT), the patient will be counted under the non-missing severity grade.

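### SAP 4.8.4 subtracts QTc values of unspecified correction method as if the formula matched; a Fridericia/Bazett mismatch would shift the change by about 10 to 12 ms at HR 70 and 34 to 42 ms at HR 100 (assumed QTcF 380 to 470 ms)

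*SAP*

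**What the plan says.** SAP 4.8.4 states that ECG parameters such as QTc "will not be converted or derived, but will be reported as provided by investigational sites". Its report of abnormal QTc covers QTcF, QTcB and QTc without a stated method. The absolute categories are >450 to 480, >480 to 500 and >500 ms at any post-baseline time. The change categories are >30 to 60 and >60 ms. For a patient whose method is unspecified at either end, "consistent correction method is assumed within a patient when calculating the change from baseline". It adds: "All ECG data will be listed, both for quantitative data and for overall impression". No check, sensitivity analysis or count of affected patients is given.

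Protocol 8.3.7 plans more than this section uses. "Three consecutive (also called triplicate) 12-lead ECGs will be performed at defined timepoints throughout the study". "ECGs will be submitted for a central review". "Assessments will include determination of heart rate and rhythm and the PR, QRS, QT, QTcF), and QTcB intervals". SAP 4.8.4 mentions neither the central review nor the triplicates.

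Two general SAP rules therefore bear on replicates. SAP 4.8: "The baseline value is defined as the last non-missing value or measurement taken up to the first dose in the study". SAP 6.1.3 takes the last of several same-day measurements where the analysis needs one value, unless another section says otherwise.

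ECG change from baseline is among the primary endpoints (protocol section 3, Table 2). SAP 3.3 restricts the analysis to Part 1 because the trial stopped early.

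**The concern.** Fridericia and Bazett agree only at a heart rate of 60. At any other rate, subtracting one from the other adds a difference that has nothing to do with the drug. By naming QTcF, QTcB and unlabelled QTc, the SAP itself allows for mixed sources, and it then assumes agreement in exactly the cases where agreement cannot be seen.

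The error is signed. At rates above 60, a Fridericia baseline with a Bazett follow-up inflates the change, and the reverse order shrinks it. With change categories cut at 30 and 60 ms, a shift of 10 to 40 ms can put a patient in the wrong one. Dose levels are small: one patient is 1/3 = 33% of a 3-patient level, 1/6 = 17% of a 6-patient level, and 1/15 = 7% if all of the roughly 15 planned Part 1 patients were combined.

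The replicate question is smaller and conditional. The protocol asks for triplicates, whose mean is steadier than a single reading, but the SAP has no rule for averaging them.

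**Working it through.** **Inputs.** The documents state no figure for this effect, so there is none to reproduce. The cut-offs come from SAP 4.8.4. QTcF and heart rate (HR) are assumptions. The upper end of 470 ms is the screening limit in protocol exclusion criterion 19 (pacemaker and bundle branch block excepted); the lower end of 380 ms is my choice.

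**Size of the shift.** QTcF = QT/RR^(1/3) and QTcB = QT/RR^(1/2), with RR = 60/HR. Hence QTcB = QTcF × k with k = (HR/60)^(1/6), and the shift is QTcF × (k − 1). QTcF and HR are those of the visit reported as Bazett.

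| HR | k | QTcF 380 | QTcF 420 | QTcF 470 |
|---|---|---|---|---|
| 60 | 1.000 | 0 | 0 | 0 |
| 70 | 1.026 | 9.9 | 10.9 | 12.2 |
| 80 | 1.049 | 18.7 | 20.6 | 23.1 |
| 90 | 1.070 | 26.6 | 29.4 | 32.9 |
| 100 | 1.089 | 33.8 | 37.3 | 41.8 |

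Below HR 60 the sign reverses: −11.4 to −14.1 ms at HR 50.

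**Mismatch alone, no true change.** A shift of t is reached at HR = 60 × ((QTcF + t)/QTcF)^6. At QTcF 420 this is HR 90.8 for 30 ms and HR 133.7 for 60 ms. At ordinary rates, therefore, the mismatch mainly moves patients who are already near a cut-off.

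**With a true change, baseline QTcF 420.**
- Fridericia then Bazett: the true rise that reads as 30 is 450/k − 420, which is 18.6 ms at HR 70 and 8.9 ms at HR 80.
- Bazett then Fridericia: the reported change is the true change minus 420(k − 1). A true +70 reads 59.1, 49.4, 40.6 and 32.7 at HR 70, 80, 90 and 100, so it drops from >60 to >30 to 60.

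**What the absolute categories catch.** Take Bazett then Fridericia, the order that hides a rise above HR 60. The post-baseline value is a true QTcF and is flagged once it passes 450.
- A rise above 60 ms stays unflagged only if baseline QTcF is below 450 − 60 = 390.
- A rise just above 30 ms stays unflagged only if baseline QTcF is below 450 − 30 = 420.
- Example of one that escapes every category: baseline QTcF 400, true +40, Bazett baseline at HR 80. The follow-up value is 440, and the reported change is 40 − 400 × 0.0491 = 20.4 ms.

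If the follow-up is instead Bazett at a rate below 60, the bounds are somewhat higher. At HR 50, k = 0.970, a QTcF of 450/0.970 = 464 reads as 450, and the first bound becomes 464 − 60 = 404.

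**Replicates, only if three records are entered.** With independent reading error of SD s, the replicate part of the SD of a change is s√2 for single readings and s√(2/3) for means of three, a ratio of √3 = 1.73. The documents give no s.

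**The case against.** The strongest objection is that the change table does not stand alone. A reader might infer that a rise masked by a mismatch leaves no trace. The documents do not support that. SAP 4.8.4 also reports absolute QTc categories that do not depend on the baseline method, and it lists all ECG data. A patient going from QTcF 420 to 490 falls in the >480 to 500 category and, in the worked cases, stays in the >30 to 60 ms change category. This stands. What remains is placement in the wrong change category, plus the narrower set of lower-baseline patients shown above.

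Second, no mismatch is shown to occur. It needs an unspecified method and a real change of formula within one patient. Exclusion criterion 19 requires a QTcF at screening, although the analysis baseline may be the later pre-dose reading. This also stands: the frequency is unknown.

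Third, central review does not prove that the assumption was avoidable. The trial stopped early, SAP 3.3 announces a reduced analysis, and central reads may be incomplete. Nor do the documents show that sites record both QT and heart rate. That is a reason to state which source is used, but not a reason to assume that formulas agree. Protocol 9.9 also plans a separate concentration-QTc assessment, which does not replace this table.

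Fourth, a reader might take the same-day rule in SAP 6.1.3 to merge ECGs that Table 4 of the protocol separates, such as those on Cycle 2 Day 1: "Pre-dose (within 30 min prior to PK sample) EOI (within 10 min prior to EOI) Post-dose* 4 h". That reading is strained. SAP 4.8.4 asks for statistics at every scheduled assessment, and 6.1.3 yields to more specific text. Likewise, loss of the triplicate mean cannot be asserted outright. If the case report form, which is not among these documents, holds one averaged value per timepoint, there is nothing to average.

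**Conclusion.** The concern holds in a limited form, and its severity is minor. SAP 4.8.4 computes a change in QTc on an assumption about the formula that it does not test. Where the assumption fails, the change is off by about 10 to 12 ms at HR 70 and 34 to 42 ms at HR 100 for QTcF 380 to 470 ms, in either direction, which is enough to cross the 30 or 60 ms cut-off. The size rests on assumed QTcF and heart rate, and the frequency is unknown. The absolute categories and listings limit the harm, and the analysis is descriptive, without hypothesis tests, and covers Part 1 only. The replicate point is a clarification that matters only if three records per timepoint are entered.

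**What to change.** In SAP 4.8.4:

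1. Base change from baseline on QTcF. Take it from the central reads planned in protocol 8.3.7 where available; otherwise derive it as QT/RR^(1/3) from recorded QT and heart rate. Use the same source at both visits within a patient. The sentence ruling out derivation must change to match.
2. Replace the sentence that assumes a consistent method. Admit to the main change table only pairs with the same known formula, show the number of patients whose change is non-computable, and keep their values in the absolute categories and listings.
3. Where replicates are recorded, average them per nominal timepoint, including baseline, and apply the outlier categories to these means. State that this takes precedence over the last-measurement rule in 6.1.3.

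The cost is SAP wording and a few lines of derivation code, with no new data collection. The downside is that patients without a usable source at both visits leave the change table, so a 3-patient level may fall to a denominator of 2. Incomplete central reads after early termination would make this more likely. The displayed non-computable count keeps that loss visible.

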4.8.5 Vital Signs

Descriptive statistics (mean, standard deviation, median, and range) for vital signs data, including systolic and diastolic blood pressure, heart rate, respiration rate, and body temperature will be calculated for the raw data and for their changes from baseline at each scheduled assessment.

Summary analyses will include data up to the start of subsequent anticancer therapy/procedure.

All vital signs data will be listed together with body weight and ECOG performance score.

4.8.6 ECOG Performance Status

ECOG results will be summarized using shift from baseline. ECOG performance score data will be listed together with vital signs and body weight.

4.8.7 Physical Examinations and Body Weight

Physical examination will be performed according to protocol. Clinically significant findings from the physical examinations will be recorded as medical history (prior to first administration of study drug) or AEs (subsequent to first administration of study drug).

Body weight will be listed together with vital signs and ECOG performance score.

4.9 Efficacy Analyses

Due to the early termination of the trial, efficacy data will be listed only. Lesion assessment data (target lesions, non-target lesions, and new lesions) and overall disease assessment will be listed.

5 Interim Analyses

NA.

6 Data handling conventions

6.1 General conventions

6.1.1 Missing data

Handling of missing/partial dates

In general, imputation of missing dates will be made for AE onset date, AE resolution date, date of death, medication start/end dates, start and end dates of prior and subsequent therapies, and date of initial diagnosis for reporting. No imputation should be done at the data level.

- If dates are completely missing, no imputation will be made.
- For any partial date with missing year, no imputation will be made.
- For missing initial diagnosis date and subsequent therapies, if only day is missing, then the 15th of the month will be used; if only year is present, then June 30th will be used. If such imputed date for initial diagnosis is on or after date of first dose, then date of first dose - 1 will be used. If such imputed date for subsequent therapies is before date of last dose, then date of last dose +1 will be used.
- If the imputed date is for an AE start date and is in the same year and month as but before the first dose date, then the first dose date will be used, or if the imputed AE start date is after the AE end date, then the AE end date will be used. If the imputed date is for an AE start date and is in the same year and month as but after the last dose date + 30 days, then the last dose date + 30 days will be used.
- If a medication date or time is missing or partially missing, so it cannot be determined whether it was taken prior or concomitantly, it will be considered as a prior and concomitant medication.
- If the imputed date is for a date of death and is before the last date that the patient is known to be alive, the latter date will be used.

Handling of missing relationship to investigational product of TEAEs

If the assessment of the relationship to investigational product is missing, then the relationship to investigational product has to be assumed and the TEAE considered as such in the frequency tables of possibly related TEAEs, but no imputation should be done at the data level.

Handling of missing severity/grades of AEs

If the severity/grade is missing for one of the treatment emergent occurrences of an AE, the maximal severity of the remaining occurrences will be considered. If the severity is missing for all the occurrences a “missing” category will be added in summary table.

No other imputation of values for missing data will be performed.

6.1.2 Unscheduled visits

Unscheduled visit measurements of laboratory data, vital signs, and ECG will be used for computation of baseline and worst values and/or grades. Re-windowing for unscheduled visits will not be performed

6.1.3 Duplicated visits

Depending on the statistical analysis method, single values may be required for each analysis window. For example, change from baseline by visit usually requires a single value per visit. Unless otherwise noted throughout the rest of this document, when a single value is needed, the following rule(s) will be used:

- If more than 1 assessment occurs during the same nominal visit, select the record closest to the nominal day for that visit.
- If there are 2 assessments that are equidistant from the nominal day, the data of the assessment after the scheduled study day will be used.
- The last measurement will be used if multiple measurements are taken on the same day.

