8.3.4 Vital Signs

Vital signs include the measurements of arterial blood pressure (systolic and diastolic), heart rate, respiratory rate, and body temperature and should be performed according to the institutional standards, see timepoints shown on Table 1. Vital signs should be measured before and after each loncastuximab tesirine infusion and each durvalumab infusion.

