9.8.3 Additional Safety Assessments

The results of scheduled assessments of vital signs, physical examinations, ECOG performance status, and 12-lead ECGs will be summarized. All data will be reported according to the nominal visit date for which it was recorded (i.e., no visit windows will be applied). Unscheduled data will be included in “worst case” summaries, which will capture a worst case across all scheduled and unscheduled visits after the first dose of study drug. All data will be listed. Further details will be provided in the SAP.

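### As written, the SAP's last-of-day rule puts post-infusion vital signs into the by-visit change from baseline on infusion days, and SAP 4.8.5 names no worst-case vital-sign summary

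*SAP*

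**What the plan says.** **Collection.** Protocol 8.3.4: "Vital signs should be measured before and after each loncastuximab tesirine infusion and each durvalumab infusion". Every infusion day therefore yields at least two same-day sets.

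**Summary.** SAP 4.8.5 says that mean, standard deviation, median and range "will be calculated for the raw data and for their changes from baseline at each scheduled assessment". It names no pre- or post-infusion timepoint. It adds: "All vital signs data will be listed together with body weight and ECOG performance score".

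**Choice among same-day values.** SAP 6.1.3 gives its own example of where one value is required: "For example, change from baseline by visit usually requires a single value per visit". Its scope is conditional: "Unless otherwise noted throughout the rest of this document, when a single value is needed, the following rule(s) will be used". The same-day rule is: "The last measurement will be used if multiple measurements are taken on the same day".

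**Baseline.** SAP 4.8: "The baseline value is defined as the last non-missing value or measurement taken up to the first dose in the study".

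**Worst case.** Protocol 9.8.3, in the paragraph that covers vital signs, physical examination, ECOG status and ECG, provides for worst-case summaries "which will capture a worst case across all scheduled and unscheduled visits after the first dose of study drug". SAP 4.8.3 repeats this for laboratory data, and SAP 4.8.4 sets QTc outlier categories. SAP 4.8.5 has no counterpart. SAP 6.1.2 nevertheless says that unscheduled vital-sign readings feed the computation of worst values.

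**The concern.** Changes from baseline in vital signs are part of a primary endpoint (protocol Section 3, Table 2). A by-visit table is useful only if its rows measure the same thing. Here baseline is a pre-dose reading, and the natural comparator at a later infusion visit is that day's pre-infusion reading. The same-day rule picks the other one. Rows for infusion days would then carry any acute infusion effect, rows for non-infusion days would not, and the profile could move up and down with the dosing calendar rather than with the patient's underlying state.

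The worst-case gap is a second, separate matter. By-visit statistics use scheduled assessments, and SAP 6.1.2 does not re-window unscheduled visits. Without a named worst-case summary, an extreme unscheduled vital sign would appear only in the listing.

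**Working it through.** The plan states no figure on this point, so none has to be reproduced. The check is a reading of the schedule against the rules, plus a count.

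**Step 1: Cycles 1-2.** Vital-sign days come from protocol Table 1. Infusion days come from protocol 4.3 and 6.3.2. The last two columns apply SAP 6.1.3 on the assumption that both readings of a day share one nominal visit.

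| Visit | Infusion | Value used | Pre-infusion value left out of the summary? |
|---|---|---|---|
| C1D1 | loncastuximab tesirine | post-infusion | No: it serves as baseline |
| C1D8 | durvalumab | post-infusion | Yes |
| C1D15 | none | non-infusion | Not applicable |
| C2D1 | loncastuximab tesirine | post-infusion | Yes |
| C2D8 | none | non-infusion | Not applicable |
| C2D15 | durvalumab | post-infusion | Yes |

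Rows that set a post-infusion reading against a pre-dose baseline: 4 of 6. Rows where a like-for-like value exists but is not summarised: 4 - 1 = 3 of 6. At C1D1 the post-infusion reading is the only post-baseline one required that day, so taking it is unavoidable.

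**Step 2: later visits.** Cycle 1 lasts 3 weeks and Cycle 2 lasts 6, so C3D1 falls at week 3 + 6 = 9, with durvalumab every 4 weeks from then. For a patient treated for the full year without delay, Day 1 infusions fall at weeks 9 + 4k, with 9 + 4k ≤ 52. So k runs from 0 to 10, giving 11 visits. Infusion visits in total: 4 + 11 = 15. Visits that lose the like-for-like value: 3 + 11 = 14. The two optional loncastuximab tesirine doses (Day 8 of Cycles 5 and 6) raise these to 17 and 16.

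**Step 3: what the mismatch does.** Suppose a patient's resting value never changes and an infusion shifts the reading by d. Change from baseline is then (rest + d) - rest = d on infusion days, and rest - rest = 0 on C1D15 and C2D8. The table shows a pattern where there is no time trend. The documents give no value for d. If d were 5 to 10 mmHg for systolic pressure, which is purely an assumption, the rows would alternate between 5 to 10 and 0. The defect in comparability does not depend on the size of d.

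**Step 4: do the documents separate the timepoints elsewhere?** Protocol Table 1 spells out pre-dose, end-of-infusion and 4-hour times for ECG and PK on loncastuximab tesirine days. The vital-signs row has one plain mark per visit day. Protocol 8.3 makes assessment before administration the default on dosing days. Protocol 8.3.4 departs from that default only by adding the second reading. Neither document defines pre- and post-infusion vital signs as distinct nominal timepoints for analysis.

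**The case against.** The strongest reply is that SAP 6.1.3 is conditional. It operates only where one value is needed and nothing else is specified, and SAP 4.8.5 speaks of scheduled assessments rather than visits. Since protocol 8.3.4 requires both readings, each could count as a scheduled assessment in its own right. SAP 4.8.4 uses the same wording for ECG, where several timed recordings on one day are clearly intended. The SAP is also to be read with the CRF, which may separate the readings.

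This stands to the extent that the documents do not settle the matter, so the conclusion must be conditional. It does not remove the problem. SAP 4.8.5 states no exception, SAP 6.1.3 offers by-visit change from baseline as its own example of a single-value analysis, and ECG has an explicit timepoint schedule (protocol Table 4) that vital signs lack. Two programmers could build different tables from the same text.

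It is also fair to say that the consequences are limited. All readings are listed. SAP 4.8.5 reports median and range as well as means. Infusion-related reactions are counted and listed as TEAEs (SAP 4.8.2.1). The analysis is descriptive, without hypothesis tests, and confined to Part 1 (SAP 3.3 and Section 4), planned at about 15 patients (protocol 9.1). All of that stands, and it caps the importance of the point.

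On the worst case, SAP 3.3 announces that protocol analyses will be selected or modified after early termination. That is general. It does not say that this summary was dropped, and SAP 6.1.2 still refers to worst values for vital signs.

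**Conclusion.** The point holds in conditional form and should be corrected. If pre- and post-infusion readings share a nominal visit, the by-visit change from baseline mixes post-infusion and non-infusion readings against one pre-dose baseline. The like-for-like value is then missing from the summary at C1D8, C2D1 and C2D15 (3 of 6 visits in Cycles 1-2) and at each later infusion visit. It rests on one assumption that the documents leave open: that the CRF does not hold the two readings as separate timepoints.

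The worst-case gap does not depend on that assumption. SAP 4.8.5 omits a summary that protocol 9.8.3 promises and SAP 6.1.2 takes for granted.

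A reader might infer two stronger things, and the documents support neither:

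- **That pre-infusion readings are discarded on every infusion day.** The C1D1 reading, when taken, is the baseline, and all the others are listed.
- **That SAP 6.1.3 has abolished the worst-case vital-sign summary.** That section does not govern worst-case calculations, and SAP 6.1.2 still presupposes them. The summary is unspecified in 4.8.5 rather than withdrawn.

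**What to change.** 1. In SAP 4.8.5, summarise pre-infusion and post-infusion vital signs as separate timepoints, and use pre-infusion values for by-visit change from baseline at infusion visits after C1D1.
2. In SAP 6.1.3, limit the last-of-day rule to true repeats at the same nominal timepoint.
3. In SAP 4.8.5, add a worst post-baseline vital-sign summary over scheduled and unscheduled values, in line with protocol 9.8.3 and SAP 6.1.2.

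A table of post-minus-pre change per infusion would be optional, since neither document promises one. The cost is a few sentences of SAP text and a small amount of extra tabulation. No new data are needed, because protocol 8.3.4 already requires both readings.
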